NCT 04612842

Engaging Older Adults in Fall Prevention Using Motivational Interviewing (MI)

Study Protocol

Oregon Health & Science University IRB #8993

PI: [name]

January 19th, 2023

One-third of older adults fall every year in the United States. Many accidental falls can be prevented through fall risk assessment and evidence-based interventions. The interventions may include advice for exercise, medication adjustment, blood pressure management, environmental modifications, and improving vision. However, older adults do not consistently follow these recommendations for a number of reasons, including their perceptions about falls and fall prevention. Emerging evidence indicates that a recommendation alone is not sufficient to engage patients in fall prevention. Yet, studies that explore alternate ways to improve patients' engagement with fall prevention are rare. Thus, we propose Motivational Interviewing (MI), an intervention known to be effective in engaging individuals in developing healthier habits, to target older adults' barriers to fall prevention.

The goal of this mixed-methods, two-arm, randomized controlled trial of MI intervention for fall prevention is to evaluate the impact of Motivational Interviewing (MI) as a follow-up care to patients who received fall prevention recommendations at Oregon Health & Science University Internal Medicine and Geriatrics Clinic provided over 12-months. Older adult participants (older than 65) who are at increased risk for falling will be enrolled into the study. Patients will be randomly assigned to two groups: MI and the standard of care group. All participants will have a baseline and 6-months study visit that will include self-report and physiologic assessment. In addition, all participants will receive study measurement phone call at 3-, and 12-months. MI will be provided via video, phone, or in-person one week after the initial visit and then monthly for 6 months. All MI sessions will be recorded and encounter notes will be completed. Purposefully selected participants' MI sessions will be transcribed for qualitative analysis.

Design

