With the inclusion of virtual encounters, a visit may be divided up into multiple sessions due to unexpected internet or living situations. For example, baseline visit is expected to be conducted in 2 sessions for the control group, and 3 sessions for the intervention group. The first session will include a review of fall prevention recommendations made at the STEADI clinic visit, self-report questions (FESI, FAB, etc), instruction about the fall calendar, and processes for the physiologic measurement during the next session (equipment, support person, environment, physical condition, internet access). The second session will be for STEADI physiologic measures (30-second sit to stand, 4-stage balance test, time up and go, and orthostatic blood pressure if possible). The participants in the intervention group will have the third session for the MI intervention #1.

Once the clinic starts normal operations, we will contact patients who received STEADI FRA and recruit them into the study. The baseline visit will be conducted in 2 (control group) or 3 (intervention group) sessions as described above.

The 6-months physiologic assessment will be conducted at the same location as the baseline location.

[Responses to fall incidents during the study data collection period]

When participants report fall incidents through their fall calendar or during study visits, the study staff will follow-up on the incident. Unless participants have a planned study visit within a month, the study staff will make a brief caring call to inquire how they are doing after the fall. We will refer them to CDC resources on fall prevention and the study packet if they are interested in information, and encourage them to talk to their provider. If the study team assesses that the fall warrant healthcare or clinical intervention beyond the scope of the research, the study may contact the provider with participants' permission.

[Updates to enhance recruitment and retention]

We will send quarterly study newsletters via email and/or postal mail to all study participants to enhance their engagement with the research. We will work with IRB and OHSU Branding Department to use approved formats. Additionally, we will also send birthday cards to participants for retention. Content and final drafts of the study newsletters and birthday cards will be submitted to the IRB for approval before distribution.

[Update 1/19/23: Study evaluation interview with enrolled participants]

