Intervention group. The intervention group participants will receive Motivational Interviewing (MI) communication about fall prevention during the 12-month study period. Interventionists will facilitate MI sessions using the MI guide (baseline version outlined in Table 32) and a participant handout, “Menu of Options for Fall Prevention,” which outlines potential topics for the discussion. MI sessions will be held at baseline, 1-week, then monthly for 6 months. MI sessions are mostly conducted via phone except the baseline and 6-months visit. The MI guide and the handout were created and tested by the study team through a feasibility study. Each MI session is targeted to be 15-minutes long. From our prior study we determined that this duration is most appropriate, short but possible to impact patient engagement with fall prevention. All of the study encounters will be audio recorded with participants’ permission and study encounter notes will be completed.

[COVID-related changes]

MI sessions will be completed via phone or video depending on the availability for the participant. Although delivery methods differ slightly, the goal of this intervention will be the same.

Table 3. Motivational Interviewing intervention guide (template for baseline study visit)

Basic approach	
Ask for permissions to discuss certain topics, use OARS (Open-ended questions, Affirming, Reflections, and Summarizing), and evoking as appropriate (make statements or ask questions to provoke alternative thinking about a situation)	
MI intervention based on readiness to change	

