[COVID-related changes]

The duration of each of the study encounter will be 60 minutes per session. Due to the unpredictable nature of virtual visits, a visit may be delivered over multiple sessions as described previously. For example, visit 1 is designed to be delivered over 3 sessions for the intervention group.

In addition, safety of in-home STEADI physiologic assessment will be ensured by having following mechanisms and can be conducted with study staff visiting their home or via video or phone.

- Participant meet the physical wellness criteria for safe testing (no fever, no dizziness felt).
- A support person will stand next to the participant throughout the tests to provide additional support in case of a fall. The support person will stop testing instantly if a participant experiences a serious imbalance.
- 30-second chair to stand test: need sturdy chair with a straight back without arm rests (seat 17" high), and a stopwatch. Enough space to sit and stand. Flat flooring without clutter. If using assistive device. Have in locked position and place it in front of the chair. Sufficient lighting. Wear glasses and hearing aides.
- 4-stage balance test: stand next to a sturdy chair.
- Timed up and go test: need 10 feet distance to walk to (marked) and chair.
- Orthostatic blood pressure: blood pressure measurement device (if do not have one, skip), bed or couch to lay down completely for 5 minutes.
- During testing visits, if a participant gets tired, testing can restart at a later time. If tiredness occurs during performance testing, participants may rest as often as needed.

The following in-person COVID-19 related safety precaution will be set for home visits and for when study office visits becomes a possibility for this study. These precautions may change according to guidelines offered by CDC, Oregon Health Authority, and OHSU.

- The participant and the study staff will be asked to take temperature and do symptom assessment before the start of the visit. This health data will be logged into REDCap. We will post-pone the visit and recommend that they contact their healthcare provider for fever>100.4, cough, fatigue, headache, other COVID-19 symptoms as outlined in CDC website <https://www.cdc.gov/coronavirus/2019-ncov/symptoms-testing/symptoms.html>.
- Participants are asked to wear masks if they have one. If not, the study will mail in the mask.

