- If the incident can be considered to be not immediate, likely, or a great threat to welfare by the study staff and the PI, study staff will encourage the participant to talk to their provider. Depending on the significance of the issue, the study staff may ask for permission for the study staff to contact the provider as an effort to minimize the harm as stated in the consent. Study staff may provide information about the suicide hotline or loneliness hotline or other resources as well.
- If it is determined that the study staff should contact the provider by the PI, participants' consent to disclose the threat will be documented in the research records. In a rare occasion where the participant refuses the study staff to communicate with the provider, PI will consult the study's mentors, DSMP, or IRB appropriately.

In the case that the disclosure of research information is consented by the participant to reduce potential threat to the welfare, we will only communicate minimally necessary information so that

the participant can receive needed services or obtain appropriate consultations based on American Psychologists Association's 2002 Ethics Code (<https://www.apa.org/monitor/jan03/10ways>)

Benefits. Participants will receive transportation cost and \$15 for each of their study visits and \$5 for participating in each of 7 study phone or video calls regardless of their performance in their fall prevention behaviors, for a maximum total incentive payment of \$65(for the intervention group). The control group participant will be paid maximum of \$35. There is a chance that participant incentives may influence patients' engagement with fall prevention activities. Thus, we will remind participants at every encounter that the payment is to recognize their time to participate in the study, and their performance on fall prevention behaviors will not influence the payment. Additionally, we will evaluate the influence of study payment at the end-of-the-study feedback opportunity from participants.

The proposed study examines the impact of MI for STEADI patients. This study will identify long-term impact of the STEADI intervention, and to examine the impact on MI in fall-related patient outcomes.

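### Does taking the 3-month self-reports at the same time point as a Motivational Interviewing session, with order and assessor unstated, call for a change to the plan?

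*Combined protocol and SAP*

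**What the plan says.** **Schedule.** Table 1 has one 3-month column (T4) with encounter type Phone. It holds MI session 5, for the intervention group only, and the self-report measures, for both groups. The overview describes the measurement contact separately from MI: "all participants will receive study measurement phone call at 3-, and 12-months". For MI, the Intervention group section says "MI sessions will be held at baseline, 1-week, then monthly for 6 months" and "MI sessions are mostly conducted via phone except the baseline and 6-months visit".

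**Six months.** The overview says "All participants will have a baseline and 6-months study visit that will include self-report and physiologic assessment", and Table 1 places MI session 8 in the same column. The COVID-related changes under Data and Specimens add that "a visit may be delivered over multiple sessions as described previously".

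**Baseline.** The COVID-related change under Study measurements puts the questionnaires in the first session and the physical tests in the second. Then: "The participants in the intervention group will have the third session for the MI intervention #1".

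**Allocation.** The Randomization section assigns consenting participants by study ID and a randomisation sequence, 125 to each group. It does not say when this happens relative to baseline measurement, who holds the sequence or how it is concealed. Blinding is not mentioned anywhere.

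**Payment.** The Benefits section pays $15 per visit and $5 "for participating in each of 7 study phone or video calls", with a maximum of $65 in the intervention group and $35 in the control group.

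**The concern.** Engagement with recommendations, fear of falling (FES-I) and fall prevention behaviours (FAB) are all self-reported, and they concern what an MI conversation is about. If they are asked just after session 5 on the same call, the MI arm's scores include an immediate reaction that controls cannot have. If they are asked just before it by the interventionist, participants are answering their coach. Either effect follows the arm, so baseline adjustment, change scores and follow-up-only comparisons would all carry it.

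The Analysis section names no primary time point, so an affected one could become the headline result. With allocation timing and concealment also unstated, a reader cannot exclude that staff or participants knew the arm when baseline measures were taken.

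**Working it through.** No arithmetic can show that the two activities share a call, so the passages are compared first.

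**1. Does one column mean one contact?** The T0 column of Table 1 also has a single encounter type (Visit) and holds MI session 1, the self-reports and the physical tests. Study measurements divides that into two sessions for controls and three for the MI arm, with MI alone in the third. Reading one column as one contact therefore fails at the only time point the text spells out. Where order is given, it is the protective one: measures first, then MI.

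**2. Do the payments settle it?** Inputs: two visits at $15, calls at $5, maxima $65 and $35.

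| Reading | MI arm | Control | Difference |
|---|---|---|---|
| Stated in Benefits | $65 | $35 | $30 = 6 calls |
| Shared 3-month call (T1–T6 and T8 = 7 calls; control 2) | 30 + 7×5 = $65 | 30 + 2×5 = $40 | $25 = 5 calls |
| Separate call, all paid (6 MI + 2 measurement = 8; control 2) | 30 + 8×5 = $70 | 30 + 2×5 = $40 | $30 = 6 calls |
| Separate call, one measurement call unpaid (6 MI + 1 = 7; control 1) | 30 + 7×5 = $65 | 30 + 1×5 = $35 | $30 = 6 calls |

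The shared-call reading reproduces $65 and misses $35. Separate calls reproduce both only if one measurement call goes unpaid. The payments support neither reading firmly.

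**3. Do the clocks agree?** Study measurements and Control group count the 3-, 6- and 12-month measures from the STEADI clinic visit. The overview counts MI from the initial study visit. The gap between the two can reach a year, so under the clinic-visit clock the 3-month measures and session 5 need not coincide. That clock cannot be literal for late recruits, whose 3- and 6-month measures would precede baseline. These passages need reconciling, but as an inconsistency of wording.

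**4. What could a shared contact do?** The documents give no figure for a shift d in MI-arm scores, so d is assumed to be 0.05 to 0.20 SD. For a two-sided 0.05 t-test with no true effect, the noncentrality is d√(n/2) on 2n − 2 degrees of freedom, with n per arm. The planned n is 125. The other value, 101, is the MI-arm number in Appendix 2, with equal arms assumed.

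| d (SD) | d/0.31 | Rejection rate, n = 125 | Rejection rate, n = 101 |
|---|---|---|---|
| 0.05 | 16% | 0.068 | 0.064 |
| 0.10 | 32% | 0.124 | 0.109 |
| 0.20 | 65% | 0.350 | 0.293 |

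The 0.31 is the inpatient effect size quoted under Number of subjects. If both 3 and 6 months were affected, an equal-weight mean of the three follow-ups would carry (d + d + 0)/3 = 2d/3, and 12 months alone would carry none. These figures show sensitivity to an assumption. They are not evidence that the shift exists.

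**The case for a change.** The strongest contrary case is that a shared call is the plain reading of Table 1, that seven paid calls fit T1–T6 plus T8 exactly, and that the clinic-visit clock is unworkable for people recruited up to a year later. The baseline order is written for baseline only, and nothing says that interventionists do not collect outcomes. Putting this right looks cheap: "All of the study encounters will be audio recorded" (with permission), so order could be coded for up to 101 × 2 = 202 contacts, about 17 hours at an assumed 5 minutes each.

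Much of this stands. The coincidence of time points at 3 and 6 months is real, the silence on order, assessor, blinding and concealment is real, and a published report should describe what was done. What does not stand is the step from silence to a design fault. Appendix 2 lists a participant encounter procedure guide and a data collection tool, where order and staffing would naturally be recorded, and nothing indicates that arms were disclosed early.

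The possible remedies add little. A separate assessor is an extra resource and could serve only contacts still to come, whereas Appendix 2 already describes 101 people allocated to MI and the intervention as provided. Coding the recordings and tabulating allocation dates report conduct and need no change to the plan. A sensitivity analysis subtracting a fixed amount from MI-arm scores would rest on an assumed shift and run the wrong way for FES-I, where higher scores are worse. It would flatter MI on the outcome used for the sample size.

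**Conclusion.** No change to the plan follows. This is missing detail that analysts and staff can fill sensibly: self-reports before MI, as at baseline, with results shown by time point and the allocation procedure described as carried out. No stated rule gives a wrong comparison.

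Two of three follow-up self-report time points coincide with an MI session in one arm, and one does not. The 6-month overlap is the less certain of the two because visits may be split. The 12-month comparison is free of this particular problem, although a smaller effect there could equally reflect waning. The error rates of roughly 6% to 35% depend wholly on the assumed shift of 0.05 to 0.20 SD. The conclusion rests on treating Table 1 columns as time points and on the absence of any sign of early disclosure. Evidence that questionnaires routinely followed MI on the same call would make the 3-month result, and possibly the 6-month result, harder to interpret.

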Intervention and control groups						
Self-report measures*	X		X		X	X
Physiologic measures**	X				X	
Fall rates (mail-in)	X	X	X	X	X	X
Notes: Self-report measures* : Fall Prevention Patient Engagement Scale, Fall Efficacy Scale International, Fall Behavioral Scale, Patient Activation Measure. Physiologic measures** : Timed Up and Go, 30-Seconds Sit-to-Stand, & 4-Stage Balance Test. E : Documented in study encounter notes (narrative descriptions of behavior change topic, behavioral goal, readiness to change, importance, confidence, commitment, barriers & facilitators for change, change from the last study encounter, satisfaction).						
wk : week, m : month						
⁺ : Visits: includes 3 options: in-home (virtual and in-person) & study office in-person visits						

Study population

Number of subjects. We estimated the sample size based on the key primary outcome measure, fear of falling as measured by FES-I, which has a reported effect size ranging from .03 to .42 depending on the setting and the type of intervention. The PI's MI intervention with inpatients found an effect size of .31 with high fall-risk inpatients. Using the power of 80% and alpha of 0.05, we need a minimum of 120 participants for an independent t-test calculation. To account for attrition, we aim to enroll 250 participants.

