- Patients who have sensory difficulty with verbal communication (hard-of-hearing despite the use of hearing aids or speech is hard to understand despite a talking device)
- Patients who are unable to stand safely without assistance by others
- Life-expectancy of less than 3-months
- Patients participating in other studies that may impact fall-related behavior change

The consent process. The study consent will be signed during the in-person encounter or via-mail. The consent form includes permission for the study to record the study encounters and access medical records, and for participants to take part in low-risk physiologic and self-reported measures (surveys), and modest compensation for their time.

[COVID-related changes]

We will consent potential participants using phone, video, mail, and email (depending on their preference) (and in-person if social distancing precautions are lifted) using the study information sheet and request waiver of documentation of the consent as an alternative proposed in <https://www.ohsu.edu/research-integrity/irb-frequently-asked-questions-faqs>. This change is made because we are changing the protocol to be remote to maintain social distancing precaution related to covid-19, and getting signed consent from older adults remotely will be challenging. Information sheet will only be used during modified operations. Once normal operations resume, written consent will be obtained for face to face encounters with participants.

This study is a minimal risk study as all physical measures in this study are the same ones they received as part of routine healthcare and pose no additional risk.

We will document in redcap that a consent discussion was held and participant's agreement to participate. We also request waiver of the signature for the HIPAA authorization with modification (expanding the provision for the study to document participants' contact information and basic demographics).

Randomization. Participants who consent to the study will be randomly assigned to two groups based on their study ID to either the intervention group (n=125) or the control group (n=125) using the randomization sequence.

Study procedures

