Appendix 2: Document Roadmap for Follow-up on STEADI patients

Study Documents
Patient Invitation Letter
Study Flyer
Patient Consent Form
Data Collection & Intervention
Draft Data Collection Tool
Participant Encounter Procedure Guide
Patient Fall Calendar
“Menu of Options for Fall Prevention”

[Added 12/30/22] Addition of qualitative study to 3. Follow-up on STEADI patients: Understanding how motivational interviewing intervention engages older adults in fall prevention behavior changes.

The third element of the STEADI research involved following up on patients who were given STEADI fall prevention recommendations and to examine the impact of a patient communication approach, motivational interviewing (MI). This addition proposed on 12/30/22 will seek to examine how MI engages older adults in fall prevention behavior changes. The findings will inform the essential aspects of MI to be incorporated into future research studies and clinical practices.

Design

We will use a qualitative research approach to understand how MI engages older adults in fall prevention behavior changes with MI intervention that was provided for the intervention group of the STEADI follow-up patients.

Study population

One hundred and one older internal medicine patients enrolled in the STEADI follow-up study and randomly allocated to the intervention group. The study team will select participants for this qualitative study using qualitative and quantitative data collected from the STEADI follow-up study to represent high- and low-change with maximum variation for the analysis.

Study procedures

We will conduct qualitative interviews with purposefully selected individuals to examine how MI engages individuals in fall prevention behaviors. Each interview session is expected to be about thirty minutes. The interview questions and prompts will be based on questions identified from analysis of MI conversations from the STEADI follow-up study. The draft interview questions is included with this modification request. The qualitative interview will be conducted via phone or video call and will be recorded and transcribed.

Data and Specimens

Source of materials. We will obtain additional verbal consent for the qualitative interview (included with this modification proposal) with selected participants who have completed the STEADI follow-up study as the intervention group participants.

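### The stated minimum of 120 participants for 80% power does not follow from any effect size the protocol names; read plainly, it gives 39% power at .31 and 63% at .42

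*Combined protocol and SAP*

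**What the plan says.** The paragraph on the number of subjects, under Study population in the combined protocol and SAP, holds the whole calculation.

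- Outcome: "We estimated the sample size based on the key primary outcome measure, fear of falling as measured by FES-I".
- Published effects for that outcome: "which has a reported effect size ranging from .03 to .42", depending on setting and type of intervention.
- The principal investigator's own motivational interviewing study with inpatients: it "found an effect size of .31 with high fall-risk inpatients".
- Result: "Using the power of 80% and alpha of 0.05, we need a minimum of 120 participants for an independent t-test calculation".
- Enrolment: "To account for attrition, we aim to enroll 250 participants".

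The Randomization paragraph allocates 125 to each arm. Appendix 2 (Study population), added in December 2022, describes the qualitative sample as "One hundred and one older internal medicine patients enrolled in the STEADI follow-up study and randomly allocated to the intervention group"; it does not give the size of the control arm.

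Five inputs are absent: the effect size that produced 120, its metric, the sidedness of the test, whether 120 is a total or per arm, and the attrition rate. The Analysis section does not supply them; it mentions descriptive statistics and names no test.

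**The concern.** With test, alpha, power, allocation and candidate effect sizes all given, the figure of 120 can be checked, and it fails the check.

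As the paragraph is written, 120 completers is the floor at which the trial still has 80% power on FES-I, and the step from 120 to 250 is an allowance for dropout. A reader would conclude that about half the sample could be lost without cost to power. If the floor is really much higher, a null FES-I result could be reported as coming from a trial with 80% power at the cited effects when it did not have that power.

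**Working it through.** **Inputs.** From the paragraph on number of subjects: alpha 0.05, power 80%, independent t-test, effect sizes .03, .31 and .42. From the Randomization paragraph: equal arms. Assumed for the plain reading, because not stated: two-sided test, effect size is a standardized mean difference d, 120 is the total (60 per arm).

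**Attempt to reproduce 120.** The normal approximation for the number per arm is

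n = 2(z₀.₉₇₅ + z₀.₈₀)² / d² = 2(1.95996 + 0.84162)² / d² = 15.698 / d²

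- d = .31: 15.698 / 0.0961 = 163.35, so 164 per arm. The exact noncentral t gives 165 per arm, 330 in total.
- d = .42: 15.698 / 0.1764 = 88.99, so 89 per arm. Exact: 90 per arm, 180 in total.
- d = .03: about 17,442 per arm. Exact: 17,443 per arm, 34,886 in total.

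None is 120. The other readings, all for 80% power and by exact t, do not give 120 either:

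| Reading | at .03 | at .31 | at .42 |
|---|---|---|---|
| d, two-sided, total | 34,886 | 330 | 180 |
| d, one-sided, total | 27,480 | 260 | 142 |
| d, two-sided, per arm | 17,443 | 165 | 90 |
| d, one-sided, per arm | 13,740 | 130 | 71 |
| Cohen's f (d = 2f), two-sided, total | 8,724 | 84 | 48 |
| Correlation r (d = 2r/√(1−r²)), two-sided, total | 8,716 | 76 | 40 |

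Taking .03 as eta-squared gives 256 in total two-sided and 202 one-sided. A paired or one-sample test needs 84 at .31 and 47 at .42 (two-sided).

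**Power with 120 in total.** The noncentrality is d√(n/2) with n = 60.

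- d = .31: .31 × √30 = 1.698. Normal approximation Φ(1.698 − 1.960) = 39.7%; exact 39.2%.
- d = .42: .42 × √30 = 2.300. Φ(2.300 − 1.960) = 63.3%; exact 62.6%.

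One-sided, the same 120 gives 52% at .31 and 74% at .42.

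**Power over the range of numbers that might be analysed** (d, two-sided, exact t):

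| Total analysed | Per arm | Power at .31 | Power at .42 | d with 80% power |
|---|---|---|---|---|
| 120 | 60 | 39% | 63% | 0.52 |
| 200 (20% loss from 250, illustrative) | 100 | 59% | 84% | 0.40 |
| 202 (101 per arm; equal control arm assumed) | 101 | 59% | 84% | 0.40 |
| 240 | 120 | 67% | 90% | 0.36 |
| 250 (no loss) | 125 | 68% | 91% | 0.36 |

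At .03, power is about 5% to 6% at 60, 120 and 125 per arm. A simulation of 40,000 trials agrees with the exact results: 39.2% and 62.5% at 60 per arm, 68.8% and 91.2% at 125 per arm.

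**Attrition implied by 250.**

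- If 120 is a total: 1 − 120/250 = 52%.
- If 120 is per arm: 1 − 240/250 = 4%.
- Loss that still leaves the 180 needed at .42: 1 − 180/250 = 28%.

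**The case against.** The best defence is that this is an unstated input, not an error. The protocol cites a range, and any value in it could have been the design effect. With 120 per arm, two-sided, 80% power corresponds to d = 0.36, which lies within the range and close to the midpoint of .31 and .42 (.365). That could be where 120 came from. But the protocol does not give that value, its wording reads as a total, and 240 of 250 leaves 4% for attrition over 12 months. If a per-arm count was meant, the sentence understates the requirement by a factor of two and still omits the effect size.

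A second defence is the metric. Read as Cohen's f, 120 in total has 92% power at .31 and more than 99% at .42; read as r, 94% and more than 99%. This stands, and it means that a shortfall in power is not proven under every reading. It does not rescue the figure, because the minimum would then be 84 or 48 (f), or 76 or 40 (r).

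Third, baseline adjustment would lower the requirement. To bring 330 down to 120 needs a baseline-to-follow-up correlation of √(1 − 120/330) = 0.80, and to bring 180 down needs √(1 − 120/180) = 0.58. The protocol names an unadjusted t-test and gives no correlation.

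Fourth, the trial plans 250, not 120. That is a fair limit on the consequences: at .42 the planned enrolment is adequate. It is also true that .31 came from inpatients while this trial enrols outpatients, and that the protocol does not say .31 drove the sizing. But .31 is the protocol's only estimate from the investigator's own motivational interviewing work, and read as d, all 250 give 68% power there two-sided and 79% one-sided.

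**Conclusion.** The concern holds. The stated minimum cannot be reproduced from any of the three named effect sizes, whether one- or two-sided, as a total or per arm, or in the other metrics tried. That conclusion needs no assumption about which reading was intended.

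The size of the shortfall does depend on the reading. Taken as a total, a standardized mean difference and a two-sided test, 120 is 60 short of the requirement at .42 (180 − 120) and 210 short at .31 (330 − 120). The planned 250 meets the requirement at .42 and falls short of it at .31 before anyone is lost. The figures for 101 per arm assume an equal control arm and count people allocated; any later loss would lower them.

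**What to change.** Drop 120 as the minimum for 80% power. State the effect size used and its metric, the sidedness, whether the count is a total or per arm, and the assumed attrition rate; then report the power the design delivers. If the metric is a standardized mean difference and the test two-sided, the text could read:

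> With 125 per arm and no attrition, a two-sided t-test at 0.05 has 80% power for d = 0.36, 68% at .31 and 91% at .42. With 100 per arm (20% attrition) it has 80% power for d = 0.40, 59% at .31 and 84% at .42.

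If another metric or a per-arm count was used, the authors should say so and give the minimum that goes with it.

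The cost is a change of protocol wording. No extra enrolment is proposed, and randomization and analysis are untouched. The drawback is that, on the plain reading, the stated power at .31 becomes visibly less favourable.
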